### 9.3. Populations

#### 9.3.1. Intent-to-Treat (ITT) Population

The intent-to-treat (ITT) population will include all randomized patients. In this population, treatment will be assigned based on the treatment to which patients were randomized, regardless of which treatment they actually received.

#### 9.3.2. Modified ITT 1 (mITT1) Population

The modified ITT 1 (mITT1) population is a subset of the ITT set. It will include all patients in the ITT population with at least 1 post baseline PBVC assessment.

#### 9.3.3. Modified ITT 2 (mITT2) Population

The modified ITT 2 (mITT2) population is a subset of the ITT set. It will include all patients in the ITT population with at least 1 post baseline efficacy assessment.

#### 9.3.4. Safety (ST) Population

The safety (ST) population will include all randomized patients who receive at least 1 dose of study drug. In this population, treatment will be assigned based upon the treatment patients actually receive, regardless of the treatment to which they were randomized.

### **9.3.5. Per-Protocol (PP) Population**

The Per Protocol (PP) population is a subset of the mITT1 population and will consist of all patients with no major protocol violations.

## **9.4. Data Handling Conventions**

Only the observed data from the patients will be used in the statistical analyses. There is no plan to estimate missing data.

The censoring rules for time to event analysis will be as described in Section [9.6.2](#).

## **9.5. Study Population**

The ITT population (see Section [9.3](#)) will be used for all study population summaries unless otherwise noted. Summaries will be presented by treatment group and for all patients.

### **9.5.1. Patient Disposition**

Data from patients screened, patients screened but not randomized (and reason not randomized), patients who are randomized (ITT), patients randomized but not treated (and reason not treated), patients in the safety, mITT1, mITT2, and PP populations, patients who complete the study, and patients who perform ET will be summarized using descriptive statistics. Data from patients who perform ET will also be summarized by reason for discontinuation using descriptive statistics.

### **9.5.2. Demographic and Baseline Characteristics**

Patient demographic and baseline characteristics, including MS history, medical history, prior medications, ECG findings, and baseline MRI will be examined to assess the comparability of the treatment groups and will be summarized using descriptive statistics. For continuous variables, descriptive statistics (number [n], mean, standard deviation, standard error, median, minimum, and maximum) will be provided. For categorical variables, patient counts and percentages will be provided. Categories for missing data will be presented if necessary.

Treatment groups will be compared for all baseline variables, using an appropriate methodology. Further details will be specified in the SAP.

## **9.6. Efficacy Analysis**

Due to the decision from 01 January 2016 to discontinue the laquinimod 1.5 mg dose arm, and a low study exposure at this time, the laquinimod 1.5 mg dose arm will be presented descriptively only, and will not be included in any inferential analyses.

In addition, all efficacy analyses will be performed based on the measurements recorded during the study treatment period, ie, data captured following an early termination visit as described in Section [3.6.7](#) will be excluded from the analyses. The data captured after an early termination visit will be used for the sensitivity analyses of the primary and secondary endpoints.

### **9.6.1. Primary Variable**

The primary variable for this study will be BA as defined by the PBVC from baseline to week 48.

### 9.6.2. Secondary Variables

#### 1. Time to CDP.

Time to CDP will be defined as increase in EDSS of  $\geq 1$  point from baseline EDSS, if EDSS at entry is  $\leq 5.0$  or increase of  $\geq 0.5$  point, if EDSS at entry is  $\geq 5.5$ . This increase should be confirmed after at least 12 weeks. Progression cannot be confirmed during a relapse.

To calculate the time of CDP, the following algorithm will be used:

Let  $E_t$  be an EDSS measurement of the patient under consideration observed at time (measured by weeks from the patient's baseline date).

Let  $E_0$  be the baseline EDSS measurement for that patient.

Let  $s = t + 12$ .

The time to CDP for the patient under consideration is defined as  $t$  if all the following conditions hold:

1. If  $0 \leq E_0 \leq 5$  then let  $\Delta = 1$ . Otherwise, let  $\Delta = 0.5$ .
2.  $E_t \geq E_0 + \Delta$ .
3. For any  $t < q_1 < s$ , if the patient's EDSS was evaluated at time  $q_1$ , then  $E_{q_1} \geq E_0 + \Delta$
4.  $E_{q_2} \geq E_0 + \Delta$  for some  $q_2 \geq s$ , and at time  $q_2$ , the patient was not experiencing a relapse.
5.  $t$  is the earliest time point during the study in which conditions 2-4 hold.

If no such  $t$  exists, then the time to confirmed progression will be right censored by the patient's last EDSS evaluation date from Part A of the study. In case time  $t$  exists without fulfilling conditions 3 and 4 because time  $q_2$  is after the patient completed Part A of the study (or performed ET), and therefore cannot be seen, then the right censored will be on time  $t$  and not in the last EDSS evaluation.

If a patient died due to MS disease progression, then this patient will be analyzed as having CDP and the time to CDP will be calculated using the onset date of progression.

If a patient died due to MS before having progression, then the time to disability progression will be censored using the date of death.

2. Time to CDP event defined by reaching at least 1 of the following 2 types of event for each individual:
  - An increase from baseline in EDSS score ( $\geq 1$  point from baseline EDSS, if EDSS at entry is  $\leq 5.0$  or increase of  $\geq 0.5$  point, if EDSS at entry is  $\geq 5.5$ ), confirmed after at least 12 weeks, **or**
  - An increase of at least 20% from baseline in the T25FW score, confirmed after at least 12 weeks

Similar algorithm to that described for CDP as measured by EDSS confirmed after at least 12 weeks will be used for definition and censoring rules of this variable.

3. Change from baseline to week 48 in the T25FW score.

4. The number of new T2 lesions at week 48.

#### **9.6.3. Exploratory/Other Variables**

- Change from baseline to week 48 in the BICAMS score (CVLT-II, BVMT-R, and SDMT)
- Time to CDP as measured by at least 1 of 4 types of events for each individual (progression cannot be confirmed during a relapse):
  - An increase from baseline in EDSS score ( $\geq 1$  point from baseline EDSS if EDSS at entry is  $\leq 5.0$ , or increase of  $\geq 0.5$  point if EDSS at entry is  $\geq 5.5$ ), confirmed after at least 12 weeks **or**
  - An increase of at least 20% from baseline in T25FW score, confirmed after at least 12 weeks **or**
  - An increase of at least 30% from baseline in the 9HPT score, confirmed after at least 12 weeks **or**
  - A decrease of at least 20% from baseline in the SDMT score, confirmed after at least 12 weeks
- Time to CDP confirmed after at least 24 weeks.
- New T1-hypointense lesions, changes in T1-hypointense lesion volume, and changes in T2 lesion volume.
- MRI, including thalamic, cortical, white matter, and cervical cord atrophy, number of cervical cord T2 lesions, and normal-appearing brain tissue average MTR.
- mRS (at week 72, visit 8).
- T25FW.
- 9HPT.
- LCVA.
- MSWS-12
- Relapses.
- Pharmacokinetic measures (determination of plasma concentration of laquinimod)
- PGx measures.
- Potential biomarker measures.
- Ancillary studies measures.

#### **9.6.4. Planned Method of Analysis**

The mITT1 and mITT2 populations (see Section 9.3) will be used for all efficacy analyses, unless otherwise noted. Summaries will be presented by treatment group.

#### **9.6.4.1. Primary Efficacy Analysis**

The primary efficacy variable for this study is BA as measured by the PBVC from baseline to week 48. This endpoint will be analyzed using the mITT1 population with at least 1 post-baseline PBVC value and will include assessments taken up to/including early termination/study completion visit (data recorded following an early termination visit will be excluded from this analysis). BA will be analyzed using baseline-adjusted repeated measures analysis of covariance (ANCOVA- SAS® PROC MIXED) in which 1 contrast will be constructed in order to compare between laquinimod 0.6 mg and placebo.

The model will be comprised from the treatment group as a class variable (2 levels). In addition to the treatment group, week (categorical), treatment by week interaction, normalized brain volume at baseline, natural logarithm of T2 lesion volume at baseline, and Country/Geographical Region (CGR) will be used as covariates. Additionally, week (categorical) will be specified as a repeated effect and unstructured (UN) correlation matrix will be used to model intra-subject correlation. In case a convergence issue will arise using the UN correlation matrix, (1) AR1 or (2) Compound Symmetry (CS) will be used to enable model convergence (in this order).

Mean values of the PBVC from baseline to weeks 24 and 48 will be summarized using descriptive statistics.

The assumption of a no treatment-by-covariate interaction will be evaluated by a separate repeated measures ANCOVA model (SAS® PROC MIXED) with the items treatment, week (categorical), week by treatment interaction, CGR, baseline, and treatment-by-baseline covariate interaction included in the model. If there is evidence of treatment-by-covariate interaction ( $p \leq 0.10$ ), further exploration of this interaction will be done graphically/descriptively and the treatment p-values will still be reported from the main effects model (repeated measures ANCOVA from above).

The consistency of treatment effects among different CGR will be evaluated by a separate repeated measures ANCOVA model (SAS® PROC MIXED) with treatment, week (categorical), week by treatment interaction, CGR, and treatment-by-CGR interaction in the model. If there is evidence of a treatment-by-CGR interaction ( $p \leq 0.10$ ), a descriptive summary of treatment differences for each CGR will be used to identify the Country (or Countries) for which the treatment effects are consistent with the remaining countries. This will be an exploratory analysis and the treatment p-values will still be reported from the main effects model (repeated measures ANCOVA from above).

#### **9.6.4.2. Sensitivity Analyses**

The robustness of the primary analysis results will be explored by applying it, as described in the previous section, to the PP population as well. In addition the, following sensitivity analysis will be performed:

- Repeat the primary analysis without introduction of covariates except for the treatment group, week, and treatment by week interaction.
- Repeat the primary analysis when introducing additional baseline covariates variables that differ appreciably between the treatment groups, if any. The list of baseline measurements will be provided in the SAP.

- Repeat the primary analysis while including observations that were recorded following an early termination visit.

#### 9.6.4.3. Secondary Efficacy Analysis

- a. Time to CDP as measured by EDSS confirmed after at least 12 weeks will be analyzed using the ITT population and data from all the study assessments up to/including early termination/study completion visit (data recorded following an early termination visit will be excluded from this analysis). This analysis will be performed using a baseline adjusted Cox's proportional hazards regression model (SAS® PROC PHREG) in which 1 contrast for comparing laquinimod 0.6 mg to placebo will be constructed. In addition to treatment group, categorical EDSS at baseline ( $\leq 4.5$  or  $> 4.5$ ), age at baseline, natural logarithm of T2 lesion volume at baseline, and CGR will be used as covariates.

The adequacy of the proportional hazards assumption will be confirmed by including 1 time-dependent covariate of dose (as dummy variable) by log (time) interactions in the analysis model and testing each of them at the 5% level. In case the proportional hazards assumption will be rejected, the log rank test (SAS® PROC LIFTEST) will be used for statistical inference.

- b. Time to CDP, confirmed after at least 12 weeks as measured by EDSS or T25FW will be analyzed using the ITT population and data from all the study assessments up to/including early termination/study completion visit (data recorded following an early termination visit will be excluded from this analysis). This analysis will be performed using baseline adjusted Cox's proportional hazards regression model (SAS® PROC PHREG) in which 1 contrast for comparing laquinimod 0.6 mg to placebo will be constructed. In addition to treatment group, categorical EDSS at baseline ( $\leq 4.5$  or  $> 4.5$ ), age at baseline, T25FW at baseline, natural logarithm of T2 lesion volume at baseline, and CGR will be used as covariates.

The adequacy of the proportional hazards assumption will be confirmed by including 1 time-dependent covariate of dose (as dummy variables) by log (time) interactions in the analysis model and testing each of them at the 5% level. If the proportional hazards assumption will be rejected, the log rank test (SAS® PROC LIFTEST) will be used for statistical inference.

- c. Change from baseline in the T25FW score at week 48 will be analyzed on the mITT2 population and will include assessments taken up to/including early termination/study completion visit (data recorded following an early termination visit will be excluded from this analysis). Since this variable might not follow normal distribution, the ranked values of this measurement will be defined and analyzed using baseline adjusted repeated measures ANCOVA (SAS® PROC MIXED) in which 1 contrast will be constructed in order to compare between laquinimod 0.6 mg and placebo. In addition to treatment group, T25FW score at baseline and CGR will be used as covariates. Due to the fact that the ANCOVA model will use ranked values and not the actual changes in the T25FW, Hodges-Lehmann estimates will be used in order to present the magnitude of the treatment effect and the corresponding two-sided 95% confidence.

d. The number of new brain T2 lesions at week 48 will be analyzed using the mITT1 population with at least 1 post-baseline T2 scan available if it was performed at least 36 weeks under treatment and will include assessments taken up to/including early termination/study completion visit (data recorded following an early termination visit will be excluded from this analysis).. This analysis will be performed using baseline adjusted negative binomial regression model (SAS® PROC GENMOD) in which 1 contrast for comparing laquinimod 0.6 mg to placebo will be constructed. In addition to the treatment group, the natural logarithm of T2 lesion volume at baseline, age at baseline, and CGR will be used as covariates.

All the secondary analyses mentioned in this section will be repeated while including observations that were recorded following an early termination visit.

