- All patients will undergo brain and cervical spinal cord MRI scans at week 0 (without and with Gd), week 24 (without Gd), and week 48 (without Gd). ET visit will include MRI for patients who prematurely terminate treatment subsequent to the week 36 visit and prior to week 48.
- EDSS and FSS will be performed at screening, week 0, and every 12 weeks until completion/ET, if applicable.
- Timed 25-foot walk (T25FW), 9-Hole Peg test (9HPT), and symbol digit modalities test (SDMT) will be performed at week 0, and every 12 weeks until completion/ET, if applicable. At weeks 0, 48, and every 48 weeks thereafter, SDMT will be performed as part of the Brief International Cognitive Assessment for Multiple Sclerosis (BICAMS) assessment.
- BICAMS, including SDMT, will be evaluated at weeks 0, 48, and every 48 weeks thereafter.
- Low contrast visual acuity (LCVA) will be assessed at weeks 0 and 24 and every 24 weeks until completion/ET, if applicable.
- Walking ability will be assessed by the 12-Item Multiple Sclerosis Walking Scale (MSWS-12) at weeks 0 and 12 and every 12 weeks until completion/ET.
- Ancillary studies:
  - Cerebrospinal fluid (CSF) (to be performed in selected sites) will be collected from all patients who signed an appropriate, Ethic Committee (EC) approved informed consent form, at week 48.
  - Optical coherence tomography (OCT) evaluation (to be performed in selected sites) will be performed in all patients who signed an appropriate, EC approved informed consent form, at weeks 0, 48, and 96 to assess retinal thickness.

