## EXPANDED DISABILITY STATUS SCALE (EDSS)

The EDSS step should not be lower than the score of any individual FS, with the exception of the Visual and Bowel/Bladder FS before conversion.

**EDSS steps from 0 up to 4.0** should not change compared to the previous examination, unless there is a change by one grade in at least one FS score.

**EDSS steps from 0 up to 1.5** can only apply if ambulation is "unrestricted".

**EDSS steps from 2.0 up to 5.0** are defined by the Functional System (FS) scores and/or walking range restriction. As an example, EDSS step 5.0 is possible with an unrestricted ambulation. EDSS steps from 2.0 up to 4.0 does only apply in individuals when at least "fully ambulatory" (able to walk  $\geq 500$  meters). If ambulation is assessed as "restricted" the pyramidal or cerebellar FS must be  $\geq 2$ .

**EDSS steps  $\geq 5.5$**  are exclusively defined by the ability to ambulate, the assistance required or the use of a wheelchair.

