7.4. Secondary Efficacy Variables and Analysis

7.4.1. Time to CDP as measured by EDSS.

Time to CDP will be defined as increase in EDSS of ≥ 1 point from baseline EDSS, if EDSS at entry is ≤ 5.0 or increase of ≥ 0.5 point, if EDSS at entry is ≥ 5.5 . This increase should be confirmed after at least 12 weeks. Progression cannot be confirmed during a protocol defined relapse.

To calculate the time of CDP, the following algorithm will be used:

Let E_t be an EDSS measurement of the patient under consideration observed at time (measured by weeks from the patient's baseline date).

Let E_0 be the baseline EDSS measurement for that patient.

Let $s = t + 12$.

The time to CDP for the patient under consideration is defined as t if all the following conditions hold:

1. If $0 \leq E_0 \leq 5$ then let $\Delta = 1$. Otherwise, let $\Delta = 0.5$.
2. $E_t \geq E_0 + \Delta$.
3. For any $t < q_1 < s$, if the patient's EDSS was evaluated at time q_1 , then $E_{q_1} \geq E_0 + \Delta$
4. $E_{q_2} \geq E_0 + \Delta$ for some $q_2 \geq s$, and at time q_2 , the patient was not experiencing a relapse (i.e. q_2 is not between onset and stabilization date of a relapse).
5. t is the earliest time point during the study in which conditions 2-4 hold.

If no such t exists, then the time to confirmed progression will be right censored by the patient's last EDSS evaluation date from Part A (or part B if the data from both part A and part B is used for analysis) of the study. In case time t exists without fulfilling conditions 3 and 4 because time q_2 is after the patient completed Part A (or part B if the data from both part A and part B is used for analysis) of the study (or performed ET), and therefore cannot be seen, then the right censored will be on time t and not in the last EDSS evaluation.

If a patient died due to MS disease progression, then this patient will be analyzed as having CDP and the time to CDP will be calculated using the onset date of progression.

If a patient died due to MS before having progression, then the time to disability progression will be censored using the date of death.

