Time to CDP as measured by EDSS confirmed after at least 12 weeks will be analyzed using the ITT population and will include data from all the study assessments done up to seven days after the last dose of the study drug (all the following assessments will be excluded from this analysis). This analysis will be performed using a baseline adjusted Cox's proportional hazards regression model (SAS® PROC PHREG) in which 1 contrast for comparing laquinimod 0.6 mg to placebo will be constructed. In addition to treatment group, categorical EDSS at baseline (≤ 4.5 or > 4.5), age at baseline, natural logarithm of T2 lesion volume at baseline, and CGR will be used as covariates. The SAS code for this analysis is as follows:

```

PROC PHREG;
  CLASS ARM EDSSBASE CGR;
  MODEL TIME_TO_PROGRESSION*CENSOR(1,2,3)=ARM EDSSBASE AGE LT2BASE CGR / COVB RL;
  CONTRAST 'Laq 0.6 to Plb' ARM 1 / ESTIMATE=EXP;
  WHERE ARM in ('Laquinimod 0.6 mg', 'Placebo');
RUN;

```

In case the above model will not converge due to CGR variable, then CGR will be removed from the model.

The adequacy of the proportional hazards assumption will be confirmed by including a time-dependent covariate of laquinimod 0.6 mg (as dummy variables) by log (time) interaction in the analysis model and testing it at the 5% level. In case the proportional hazards assumption will

be rejected, the log rank test (SAS® PROC LIFTEST) will be used for statistical inference. The SAS code for checking the proportional hazards assumption is as follows:

```
PROC PHREG;
  CLASS ARM EDSSBASE CGR;
  MODEL TIME_TO_PROGRESSION*CENSOR(1,2,3)=ARM ARMT EDSSBASE AGE LT2BASE CGR ;
    ARMT = ARM*log(TIME_TO_PROGRESSION);
    PROP_HAZARDS_TEST_LAQ_0_6: test ARMT;
    WHERE ARM in ('Laquinimod 0.6 mg', 'Placebo');
  RUN;
```

In case the above model will not converge due to CGR variable, then CGR will be removed from the model.

In addition, patients with CDP will be summarized using descriptive statistics. The time to CDP will be presented by Kaplan-Meier curves stratified by treatment group.

EDSS scores and changes from baseline to each visit will be summarized using descriptive statistics.

All analyses presented in the section will be repeated to include both part A and part B when the study is completed.

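### Baseline T25FW is left out of the Cox model for EDSS-confirmed progression, the first secondary endpoint; adding it may recover a little power at almost no cost

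*Protocol*

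**What the plan says.** Model for CDP by EDSS. After treatment and EDSS (up to 4.5, or above), Protocol 9.6.4.3(a) states that "age at baseline, natural logarithm of T2 lesion volume at baseline, and CGR will be used as covariates". The SAP 7.4.1 code has the same terms: "MODEL TIME_TO_PROGRESSION*CENSOR(1,2,3)=ARM EDSSBASE AGE LT2BASE CGR / COVB RL".

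Next model. For CDP by EDSS or T25FW, Protocol 9.6.4.3(b) has one more term: "age at baseline, T25FW at baseline, natural logarithm of T2 lesion volume at baseline, and CGR will be used as covariates". SAP 7.4.2 matches it.

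Availability. The protocol synopsis says that the "Timed 25-foot walk (T25FW), 9-Hole Peg test (9HPT), and symbol digit modalities test (SDMT) will be performed at week 0", and the baseline column of Protocol Table 5 includes T25FW.

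Event rule and scale. SAP 7.4.1 requires a rise of at least 1 point "if EDSS at entry is ≤ 5.0 or increase of ≥ 0.5 point, if EDSS at entry is ≥ 5.5". Protocol Appendix G says that EDSS steps from 5.5 up "are exclusively defined by the ability to ambulate, the assistance required or the use of a wheelchair".

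Place in the plan. SAP 5.3 tests the secondaries in a fixed order after a significant primary result, with CDP by EDSS first. Each later endpoint is tested only if the one before it reaches p ≤ 0.05. Protocol 9.7 has no such order, but the SAP Preface says that the SAP prevails.

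**The concern.** Leaving a prognostic covariate out of a Cox model moves the estimated treatment log hazard ratio towards zero. Power falls, although the test of no effect stays valid. Walking speed at entry is a plausible covariate here because, for part of the population, the event itself is a walking threshold. A two-level EDSS term describes walking only coarsely. The model already carries age and T2 volume, which are not components of EDSS, so its covariates were not confined to the outcome's own baseline.

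At stake is some power on the endpoint that gates the other three secondaries in the SAP. The plan states no power for CDP.

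**Working it through.** **1. The plan's own power figure.** Protocol 9.2 gives 84% for PBVC with 126 per arm, difference 0.3 and SD 0.8, two-sided 5%. The standard error is 0.8 × √(2/126) = 0.1008. Then 0.3/0.1008 = 2.976, and Φ(2.976 − 1.960) = 84.5%, so it reproduces. This figure concerns the primary endpoint only.

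**2. Who faces a walking threshold.** Entry EDSS runs from 3.0 to 6.5. Applying the event rule gives:

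| Entry EDSS | 3.0 | 3.5 | 4.0 | 4.5 | 5.0 | 5.5 | 6.0 | 6.5 |
|---|---|---|---|---|---|---|---|---|
| Lowest step that counts | 4.0 | 4.5 | 5.0 | 5.5 | 6.0 | 6.0 | 6.5 | 7.0 |

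From entry 4.5 upward the step to be reached is 5.5 or more, so it is defined by walking. For entry 3.0 to 4.0 the step lies between 4.0 and 5.0, which Appendix G bases on functional systems, walking range or both.

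**3. Power for CDP before any change.** The event counts are assumed: 20% or 30% of 280 patients, that is 56 or 84 events. The hazard ratio of 0.60 is borrowed from the 40% reduction in the relapsing-remitting subgroup with EDSS above 3 (Protocol 1.1.1) and is not a design input. Schoenfeld's formula with 1:1 allocation is power = Φ(√d/2 × |ln HR| − 1.960), with ln 0.60 = −0.511.

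- d = 56: 3.742 × 0.511 = 1.911, power 48%.
- d = 84: 4.583 × 0.511 = 2.341, power 65%.
- For 80% power: 4 × (1.960 + 0.842)² / 0.511² gives 121 events. At hazard ratio 0.66, 182 events are needed.

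**4. Adding T25FW alone.** Simulation of 280 patients, 1:1, true log hazard ratio −0.511, follow-up 48 to 120 weeks, 1,500 trials per row. T25FW was simulated as a normal score with a linear effect on the log hazard. Both models were fitted to the same simulated trials; CGR was not simulated. All prognostic inputs are assumptions. Cells show power in %, planned model → planned model plus T25FW.

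| HR for EDSS ≥5.5 | HR per SD of T25FW | Share at EDSS 5.0 | Correlation of T25FW with EDSS | 20% events | 30% events |
|---|---|---|---|---|---|
| 1 | 1 | 7% | 0.6 | 47.1 → 47.2 | 62.6 → 62.7 |
| 1.5 | 1.2 | 7% | 0.6 | 46.9 → 46.9 | 65.1 → 64.8 |
| 2 | 1.5 | 7% | 0.6 | 46.2 → 47.1 | 60.1 → 62.1 |
| 2 | 1.5 | 15% | 0.6 | 41.9 → 43.9 | 57.9 → 60.1 |
| 3 | 1.5 | 15% | 0.6 | 41.4 → 44.3 | 57.7 → 61.5 |
| 2 | 2 | 15% | 0.3 | 43.4 → 47.3 | 52.9 → 59.4 |

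The changes run from −0.3 to +3.9 points, apart from +6.5 in the last cell. Moving the EDSS cut to 5.0/5.5 as well takes that cell to 61.6% (+8.7).

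**5. Mechanism.** In that same cell the mean log hazard ratio goes from −0.465 to −0.511, while its standard error goes from 0.226 to 0.228. In the no-effect row with 20% events the standard error goes from 0.280 to 0.281. The gain is reduced attenuation, not a smaller standard error.

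**The case against.** The omission follows a recognisable rule. Baseline T25FW enters when T25FW is part of the endpoint: EDSS or T25FW, the four-event composite (SAP 7.5.3) and T25FW alone (SAP 7.5.20). This stands: use in the next model does not show an oversight.

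The link between T25FW and EDSS is also looser than it looks. Upper EDSS steps rest on walking distance and assistance, whereas T25FW is speed over 25 feet with aids allowed (Protocol Appendix H). No correlation is given, and the threshold argument does not cover entry at 3.0 to 4.0. This too stands, and it is why the gain can only be given as a range that includes zero.

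Events, not covariates, are the main limit: 48% to 65% power on the assumed counts. If proportional hazards is rejected, inference moves to a log-rank test for which SAP 7.4.1 specifies no adjustment, and any gain is lost. Both are true. They limit the benefit without creating a cost.

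Three stronger readings are tempting, and none is supported.

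- A reader might infer that precision is being given away. The standard error stays level or rises by about 1%.
- A reader might infer that the EDSS cut at 4.5 must be moved, because patients at 5.0 share a category with those under the 0.5-point rule. The documents give no event rates by entry EDSS. In simulations at hazard ratio 0.66 with about 65 events, recutting alone added 0.2% to 1.2% in effective information (squared ratio of mean Z). A separate level for 5.0 could be small and add to the convergence trouble that SAP 7.4.1 already provides for.
- A reader might infer that T25FW should be logged in the EDSS-or-T25FW model too. No gain has been shown.

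**Conclusion.** The point holds as a modest efficiency recommendation. The planned model is pre-specified and its test is valid. It leaves out a baseline measure that the trial already collects and that plausibly predicts the event for patients entering at EDSS 4.5 or above.

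The expected gain is roughly 0 to +4 power points. Only a doubling of hazard per SD of T25FW, weakly correlated with EDSS and with 30% of patients having an event, gave more: +6.5 for T25FW alone, and nearly +9 only when the EDSS cut was moved as well. If T25FW is not prognostic, almost nothing is lost. These figures rest on an assumed hazard ratio, event rate, EDSS distribution and prognostic strength, none of which the plan gives for this trial. The documents do not support calling the omission an error or a threat to the conclusion.

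**What to change.** Before unblinding, add the natural logarithm of baseline T25FW to the covariates in Protocol 9.6.4.3(a) and to the PHREG MODEL statement in SAP 7.4.1. Carry the term into the proportional-hazards check there, the 24-week analysis in SAP 7.5.4, which takes its covariates by reference, and the by-gender repeat in SAP 7.5.21. The log scale is a judgement: T25FW can reach the assigned 180 seconds (SAP 7.4.2), and the plan itself doubts that its change is normal. Leave the EDSS split and the EDSS-or-T25FW model as they are.

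State how a missing baseline T25FW is handled. SAP 5.5 imputes nothing for this variable, so such patients would drop out of an ITT analysis. One option is the mean of the logged values in the same baseline EDSS category, pooled over arms and computed without outcome data.

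The cost is one degree of freedom, the missing-value rule and a short SAP amendment. No new data are needed. SAP 3.5.2 keeps the codes blinded until the SAP is approved and the Part A database is locked, so the change belongs before that approval.
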